1. BACKGROUND AND SIGNIFICANCE

Radical cystectomy is the gold standard treatment for muscle-invasive bladder cancer. It involves removal of the bladder and prostate for men and anterior exenteration (including the bladder, uterus, ovaries, and part of the vagina) for women. Patients who were treated with the surgical approach report poor overall satisfaction, sexual function, urinary and bowel function, and health-related quality of life. The current NCCN (National Comprehensive Cancer Network) Clinical Practice Guidelines (version 2.2015) indicates bladder-preserving therapy with cystectomy reserved for tumor recurrence represents a safe and effective alternative to immediate radical cystectomy for muscle invasive bladder cancer.

According to the current NCCN guidelines, patients who are not surgical candidates (i.e. those with extensive comorbidities and/or poor performance status), chemoradiation can be used as a curative treatment regimen. This bladder-sparing therapy consist of (1) maximal transurethral resection of bladder tumor (TURBT), (2) induction external-beam radiation therapy with concurrent chemotherapy, (3) cystoscopic assessment of treatment response with prompt cystectomy for non-responders, and (4) active cystoscopic surveillance with salvage cystectomy at the first sign of invasive recurrence.

Retrospective studies have shown that the majority of chemoradiation patients achieves a clinical response and preserves the native bladder in >70% of patients while offering long-term survival rates comparable to contemporary cystectomy series.^{1,2}

We hypothesize that chemoradiation is non-inferior to radical cystectomy with regard to quality of life and progression free and bladder intact survival. Short of a randomized trial, any direct comparison of chemoradiation to radical cystectomy to address our hypothesis is difficult and must account for selection bias and confounding variables resulting from discordance between clinical, pathologic staging, functional status and comorbidities. Our proposed randomized pilot non-inferiority study aims to provide feasibility data for a larger randomized clinical non-inferiority trial comparing the efficacy and safety of chemoradiation and radical cystectomy.

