3. STUDY ENROLLMENT AND WITHDRAWAL

3.1 Inclusion Criteria:

3.1.1 Pathologically (histologically) proven diagnosis of primary carcinoma of the bladder (transitional cell cancer) within 8 weeks of registration. Operable patients whose tumors are primary carcinomas of the bladder and exhibit histologic evidence of muscularis propria invasion and are AJCC clinical stages T2-T4a, Nx or N0, M0

3.1.2 Patients without histologically or cytologically confirmed node metastases or any other metastases

3.1.3 Patients must have an adequately functioning bladder after thorough evaluation by an urologist and have undergone as thorough a transurethral resection of the bladder tumor as is judged safely possible.

3.1.4 Patients must be considered able to tolerate systemic chemotherapy combined with pelvic radiation therapy, and radical cystectomy.

3.1.5 History and physical examination including weight, performance status, and body surface area within 8 weeks prior to study registration

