3.3 Randomization Procedure

A total of 30 patients will be randomized to either chemoradiation group (n=15) or radical cystectomy (with or without neoadjuvant chemotherapy group, n=15). Permuted block randomization process through sequentially numbered, opaque sealed envelopes will be utilized in assigning participants into either radical cystectomy or chemoradiation group. All subjects will be randomized in blocks of size 2. A randomization list containing sequence numbers and treatment assignments will be prepared by the statistician and used as the sole basis for treatment assignments throughout the study.

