to read and consider and ample opportunity will be given to answer any questions. The participant may decline to participate, decide to participate, or take the consent home to think about participating. A copy of the signed consent form will be provided to each participant.

The potential participant will then be scheduled for a TURBT (transurethral resection of bladder tumor) with the treating urologist, which may also be the study's principal investigator or co-investigator. TURBT is the standard of care which allows the treating urologist to formally assess the extent of disease progression and also to evaluate whether the candidate can be treated with both radical cystectomy and chemoradiation treatment. Potential participant will be approached to store any leftover tissue specimens, not needed for diagnosis, into the "GU Tissue Bank" (IRB HSC20050234H). The tissue collected will be processed per standard of care, and slides or tissue blocks may be accessed later for future use in correlative studies. The leftover specimens may be used for future research studies that may include genetic testing related to bladder cancer. This banking portion is optional and not required to be in the main study. If the participant declines to participate in the optional study, any leftover specimens will be permanently de-identified through the GUTB (05-234H).

The potential participant will then return to the clinic for a routine follow-up visit to review the TURBT results and discuss treatment options with the treating Urologist within 4 weeks post-TURBT. Final eligibility will be determined during the TURBT follow-up visit. If potential participant is eligible for the study, randomization will occur. The following section outlines study procedure during the visit.

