9. DATA COLLECTION & STUDY EVALUATIONS

Medical records will be reviewed prior to “Baseline Study Visit” to confirm study eligibility. After obtaining consent, socio-demographic data will be collected through chart review and interviews. Clinical data that will be collected include but not limited to bladder cancer treatment history, tumor characteristics, stage, laboratory results, medications and co-morbidity.

Study team member or clinic staff will measure height, weight, and vital signs at each specific study time point. Research blood will be drawn at each study time point. Blood and tissue samples may be banked under the optional study (HSC20050234H GU Tissue Bank). For those participants who declined to participate in the optional study, any leftover samples will be permanently de-identified through the GU Tissue Bank (HSC20050234H) honest broker system. At the close of this study, all biological materials collected will be rolled into HSC20050234 GU Tissue Bank.

9.1 Feasibility: We will report recruitment, visit dates, adherence, attrition rates and compliance with randomization for each arm of the study

9.2 Bladder-intact survival: We will report proportion of patients who failed chemoradiation and required salvage cystectomy

9.3 Quality of life: A self-assessment questionnaire using the European Organization for Research and Treatment of Cancer (EORTC) QLQ- C30 and FACT-Bladder will be used for QOL assessment at baseline, 3, 6, 9 and 12 months.⁸

9.4 Progression free survival: This will be measured from the date of finishing chemoradiation or radical cystectomy to the date of first documentation of progression. Progression will be determined using RECIST 1.1 criteria by the treating physician based on radiographic or pathologic evidence of disease progression, or death from disease. Any documented recurrence will be considered progression.⁹ The date of progression will be recorded.

9.5 Candidate gene expression analysis: For the participants who have consented to be part of the optional study (“GU Tissue Bank HSC20050234H), a microarray analysis will be performed on all bladder tumor specimens using Agilent Technologies (Agilent SurePrint G3 Human Gene Expression 8x60K v2) Microarray. Goal is to study the landscape of 50 important candidate genes, which are involved in bladder cancer (for example-BRAF, KRAS, EGFR, FGFR).

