Categorical outcomes will be summarized with frequencies and percentages. Continuously distributed outcomes will be summarized with the sample size, mean, standard deviation, median, minimum and maximum. A consort diagram giving the number patients screened, the number of screen failures, the number randomized, the number lost to follow-up by reason, and the number completing the study by treatment arm will be created. In Aim 1a we will test the hypothesis that chemoradiation therapy is non-inferior to radical cystectomy with regard to change in quality of life at 36 months relative to baseline. In Aim 1b, we will test the hypothesis that chemoradiation is non-inferior to radical cystectomy with regard progression free survival and bladder intact survival. With regard to Aim 1a, assuming the 50% (p_2) of patients randomized to radical cystectomy and 60% (p_1) of patients randomized to chemoradiation will experience improvement in quality of life at 3 years relative to baseline and a 5% margin (Δ) of non-inferiority, this study would require $n=171$ subjects per group to attain 80% power for testing $H_0: p_1 - p_2 \leq \Delta$ versus $H_1: p_1 - p_2 > \Delta$ with $\alpha=5\%$. The non-inferiority of chemoradiation compared with radical cystectomy with regard to changes in quality of life (Aim 1a) will be assessed with Fisher's exact test. Progression free and bladder-intact survival (Aim 1b) will be summarized by treatment arm with Kaplan-Meier curves and supporting tabulations and non-inferiority will be assessed with a logrank test. The significance of treatment arm differences with regard to biomarkers (Aim 2a) will be assessed with t-tests or Wilcoxon tests. Pairwise correlations between biomarkers will be displayed overall and by treatment arm. Logistic regression will be used to find a best linear predictor of treatment arm in terms of multiple biomarkers. Biomarkers may be log transformed prior to analysis. Feasibility (Aim 2b) will be assessed with a new power and sample size calculation. If the logistic regression model fails in Aim 2a, random forests will be attempted. If the logrank test fails in Aim 1b, Fisher's exact test will be used. R (v3+, Vienna, Austria) or SAS (SAS Institute, Cary, North Carolina) software will be used throughout.

REFERENCES

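### PFS is compared without using clinical stage, which is known before randomisation and not balanced by design: the test stays valid overall, but a chance stage imbalance in 15 vs 15 would bias the estimate in either direction

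*Combined protocol and SAP*

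**What the plan says.** Section 11 summarises PFS by arm with Kaplan-Meier curves, and "supporting tabulations and non-inferiority will be assessed with a logrank test". No stratum, covariate or survival model is named. The fallback is also unadjusted: "If the logrank test fails in Aim 1b, Fisher's exact test will be used". The only regression planned is logistic, for the biomarkers in Aim 2a. No stage-adjusted PFS analysis appears anywhere, even as a sensitivity analysis.

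Section 3.1.1 admits "AJCC clinical stages T2-T4a, Nx or N0, M0". Section 3.3 fixes the size ("A total of 30 patients will be randomized to either chemoradiation group (n=15) or radical cystectomy") and the method ("All subjects will be randomized in blocks of size 2"), using one list and no stratification factor. Under Section 4.1, allocation follows review of the TURBT result: "If potential participant is eligible for the study, randomization will occur". Section 9 lists among the clinical data to be collected "tumor characteristics, stage, laboratory results, medications and co-morbidity".

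**The concern.** Blocks of 2 balance the number of patients per arm, not their stage. With 15 per arm, a gap of three or four T3-T4a patients is an ordinary outcome. If stage predicts progression, such a gap shifts the unadjusted comparison, and nothing in the plan would show by how much.

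Two things are at stake. The trial asks whether chemoradiation is no worse than cystectomy, and a lucky stage draw for chemoradiation would make it look better than it is. The pilot is also meant to inform a larger trial, so a distorted PFS estimate could carry over into that design. An adjustment added only after an imbalance has been seen would look data-driven, so it has to be specified in advance.

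**Working it through.** **The plan's own figure.** Section 11 gives one sample size, for quality of life (Aim 1a): 60% vs 50%, margin 5 points, 80% power. n = (1.960 + 0.842)² × (0.6×0.4 + 0.5×0.5) / (0.10 + 0.05)² = 7.849 × 0.49 / 0.0225 = 170.9, so 171 per group. This matches if alpha is one-sided 0.025 and the null lies at −5 points. No event count, power or margin is given for PFS, so there is no PFS figure to reproduce.

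**Assumptions not in the documents.** T3-T4a share 20-50%; stage hazard ratio (T3-T4a vs T2) 1.5-3; exponential PFS censored at 36 months; no dropout.

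**Step 1: how often the arms differ.** Treat the T3-T4a count in each arm as binomial(15, p) and sum the exact probabilities of the difference.

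| T3-T4a share | Gap of 3 or more patients (20 points) |
|---|---|
| 20% | 25% |
| 30% | 32% |
| 40% | 35% |
| 50% | 36% |

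A gap of 4 or more has probability 11-20%. With 171 per group, a 20-point gap would have a chance of about 0.02% or less, so this is a small-trial problem.

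**Step 2: what a gap does with no treatment effect.** Hand check: 12 of 30 patients (40%) are T3-T4a, split 8 and 4. With stage hazard ratio h, the ratio of mean baseline hazards is [1 + (8/15)(h − 1)] / [1 + (4/15)(h − 1)].
- h = 1.5: 1.267/1.133 = 1.12
- h = 2: 1.533/1.267 = 1.21
- h = 3: 2.067/1.533 = 1.35

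Simulation over all gaps of 3 or more agrees: the unadjusted hazard ratio averages about 1.13-1.36 against the arm with more T3-T4a patients. The logrank stratified by T2 vs T3-T4a gives about 0.97-1.04.

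**Step 3: size against noise.** As a bracket only, Section 1.1.1 quotes three-year disease-specific survival of 74% and 50% in T2 patients by response. 30 × 0.26 = 7.8 and 30 × 0.50 = 15, so about 8-15 events. The standard error of the log hazard ratio is about 2/√D: 0.71 at 8 events and 0.52 at 15. The shift is ln 1.13 = 0.12 to ln 1.36 = 0.31, roughly 0.2 to 0.6 of a standard error.

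**Step 4: both directions.** Probability of detecting harm when the true hazard ratio is 2.5 against chemoradiation (share 40%, T2 three-year PFS 65%, one-sided 5%):

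| Stage draw | Stage HR | Unadjusted | Stratified |
|---|---|---|---|
| Chemoradiation has at least 3 fewer T3-T4a | 2 | 41-43% | 55-57% |
| | 3 | 31-32% | 58% |
| Chemoradiation has at least 3 more T3-T4a | 2 | 72% | 55-57% |
| | 3 | 77% | 56-58% |
| All randomisations | 1.5 | 57.6% | 56.1% |
| | 2 | 57-58% | 58% |
| | 3 | 54-55% | 60% |

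Ranges cover repeated simulations. Two-sided type I error over all randomisations is 5.0-5.3% unadjusted and 5.1-5.3% stratified.

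**The case against.** The strongest reply is that randomisation already deals with stage. Over all possible allocations the unadjusted logrank holds its 5% level, and the two stage draws in Step 4 are about equally likely. A reader might infer that the planned test is invalid, that it systematically hides harm from chemoradiation, or that stratifying buys power. None of these is supported. The level is correct. An unfavourable draw makes the unadjusted test detect harm more often than the stratified one. The overall power change runs from a loss of 1-2 points to a gain of about 6, depending on a stage effect that the documents do not give.

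A reader might also infer that the protocol itself shows stage to drive outcome. It does not. Section 1.1.1 gives survival for T2 only, split by response. Section 1 does mention "confounding variables resulting from discordance between clinical, pathologic staging, functional status and comorbidities", but for comparisons made without randomisation, and its point about discordance suggests that clinical stage is an imperfect adjuster.

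It is also fair that this is a pilot. Two-sided power for a hazard ratio of 0.5 or 2 is only 20-26% with either analysis, and a standard logrank with no PFS margin cannot show non-inferiority, stratified or not.

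All of this stands and limits the point. It does not remove it: the trial will be run once, with one stage split, and the plan has no way to account for that split.

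**Conclusion.** The point holds as conditional bias in a small trial. In roughly a quarter to a third of randomisations (25-36%, for T3-T4a shares of 20-50%) the arms would differ by at least 20 percentage points in T3-T4a disease. The unadjusted PFS hazard ratio would then be off by an average factor of about 1.13-1.36 in either direction, if the stage hazard ratio is 1.5-3. At 1.5 the effect is small. Share and stage effect are both assumptions, so the size is a range, not a finding about this population. The case for change is that stage is available before allocation and the remedy is cheap.

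**What to change.** In Section 11, pre-specify for PFS a hazard ratio with confidence interval from a Cox/logrank analysis stratified by clinical stage at randomisation (T2 vs T3-T4a), reported beside the unstratified result. Use one binary factor only; about 8-15 events will not support more. Stage found after randomisation, such as pathologic stage at cystectomy, should not be used.

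Section 9 says only that stage is collected, so add that the clinical T category is recorded before the allocation envelope is opened. Section 4.3 ties imaging to the start of treatment, so the staging information to be used should be stated.

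The cost is a sentence or two and no new assessment. The downside should be stated too: the SD of the stratified log hazard ratio may be up to roughly 9% larger, and overall power is about unchanged (1-2 points lower if the stage hazard ratio is near 1.5, up to about 6 points higher if near 3). The missing PFS margin needs its own correction, and the pilot's PFS result remains an estimate, not a confirmatory test.

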2. HYPOTHESIS AND SPECIFIC AIMS

Multiple prospective radiation therapy protocols have evaluated bladder-preserving chemoradiation therapy approach for muscle-invasive bladder cancer (MIBC), with radical cystectomy reserved for radiation failure. Aims of bladder preservation in MIBC are to offer a quality-of-life advantage and avoid potential morbidity or mortality of RC without compromising oncologic outcomes. Because of lack of level-1 evidence, oncologic equivalence of bladder preservation modality treatments compared with RC remains unknown.

2.1 HYPOTHESIS:

We hypothesized that chemoradiation is non-inferior to radical cystectomy for treatment of MIBC.

2.2 SPECIFIC AIMS:

SPECIFIC AIM 1a To determine and quantify quality of life in patients treated with radical cystectomy and chemo radiation therapy

1b To determine and quantify progression free survival and bladder-intact survival in patients treated with radical cystectomy and chemoradiation therapy,

SPECIFIC AIM 2a To evaluate genetic markers predicting response to chemoradiation by performing tissue RNA microarrays.

2b To assess the feasibility of conducting an adequately powered non-inferiority trial of the same design via recruitment rate, patient adherence to both treatment arm, and attrition.

2.3 STUDY DESIGN:

Our study will be a pilot, prospective, single-center, randomized non-inferiority trial comparing chemoradiation therapy to radical cystectomy. Patients diagnosed with muscle invasive bladder cancer after transurethral resection of bladder tumor and are surgical candidates will be randomized to either radical cystectomy (with neoadjuvant chemotherapy if suitable candidate) or chemoradiation.

Both treatment methods are considered “standard of care” recommended by the NCCN Clinical Practice Guidelines (http://www.nccn.org/professionals/physician_gls/pdf/bladder.pdf) in treating muscle invasive bladder cancer.

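### Section 11 assigns PFS non-inferiority (Aim 1b) to a logrank test, with Fisher's exact test as fallback, but gives no PFS margin; short of showing superiority, neither test can establish non-inferiority

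*Combined protocol and SAP*

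**What the plan says.** Section 11 makes Aim 1b a formal test: "we will test the hypothesis that chemoradiation is non-inferior to radical cystectomy with regard progression free survival and bladder intact survival". After Kaplan-Meier summaries by arm, "non-inferiority will be assessed with a logrank test". A later sentence adds the fallback: "If the logrank test fails in Aim 1b, Fisher's exact test will be used". Neither sentence gives a margin, a significance level, sidedness, a hazard-ratio bound or a confidence-interval rule. What counts as the logrank test failing is not defined.

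The one margin, "a 5% margin (Δ) of non-inferiority", is introduced for Aim 1a. It goes with an assumed 50% improving after cystectomy, and "60% (p_1) of patients randomized to chemoradiation will experience improvement in quality of life at 3 years relative to baseline". From these the plan derives 171 "subjects per group to attain 80% power for testing" the Aim 1a hypotheses.

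Section 9.4 defines PFS from the end of treatment to first progression and sets no margin or event target. Section 2.2 words Aim 1b as measurement rather than testing. Section 1 describes the study as a pilot meant to supply feasibility data. Sections 3.3 and 11 fix the size at 15 per arm.

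**The concern.** The null of a non-inferiority test is that chemoradiation is worse than cystectomy by at least a stated margin. Without a margin that null cannot be written down. The ordinary logrank null is equal hazards, and the Fisher null is equal proportions.

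Three results are possible:

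- **Significant, favouring cystectomy:** shows a difference in the wrong direction.
- **Significant, favouring chemoradiation:** shows superiority, and so non-inferiority at any margin.
- **Not significant:** says nothing about whether a margin has been respected.

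With 15 patients per arm the third result is the usual one, and it becomes more likely as events become fewer. If it were reported as non-inferior PFS, lack of information would be presented as evidence on the main oncologic question.

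**Working it through.** **1. The plan's own figure.** Inputs from Section 11: p1 = 0.60, p2 = 0.50, margin 0.05, power 80%. The 171 is reproduced by taking the margin as a 5-point deficit and alpha as one-sided 2.5%:

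n = (1.96 + 0.8416)² × (0.6×0.4 + 0.5×0.5) / (0.10 + 0.05)² = 7.849 × 0.49 / 0.0225 = 170.9, so 171 per group.

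One-sided 5% would give 135. The figure is therefore sound on that reading, but it concerns a quality-of-life proportion and gives PFS no support.

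**2. How many PFS events to expect.** The documents give no PFS planning rate, so this is an assumption. With 15 per arm, exponential PFS, 36 months of follow-up, about 10% dropout and cystectomy 3-year PFS of 50-70%, mean events are 8.5 to 18 for hazard ratios (HR, chemoradiation to cystectomy) of 1 to 2. As a rough plausibility check, Section 1.1.1 quotes 3-year disease-specific survival of 74% and 50% by response in stage T2 patients. Applied to 30 patients, that is 30 × 0.26 = 7.8 to 30 × 0.50 = 15 disease deaths, before other progressions are added.

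**3. How often the logrank test is non-significant (two-sided 5%, simulated, 8,000 runs per scenario).**

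| Cystectomy 3-year PFS | HR 1.5 | HR 2 |
|---|---|---|
| 50% | 0.865 | 0.697 |
| 60% | 0.884 | 0.743 |
| 70% | 0.903 | 0.787 |

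In the middle row, HR 2 means a chemoradiation 3-year PFS of 0.60² = 36%. A separate simulation without dropout (10,000 runs per scenario) gave 0.683, 0.731 and 0.784 at HR 2 for the same three rates, and 0.642 if cystectomy 3-year PFS is 40%.

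**4. Analytic check.** With SE(log HR) = 2/√d for d events, P(non-significant) at HR 2 is 0.820 for d = 9 and 0.687 for d = 18. At HR 1.5 it is 0.907 and 0.862. If the test were one-sided at 5%, the HR 2 figures would be 0.728 and 0.569. If all 30 patients had an event, the two-sided figure at HR 2 would still be 0.525.

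**5. What the data could show.** With an observed HR of 1, the 95% CI is exp(±1.96 × 2/√d): 0.27 to 3.69 at 9 events and 0.40 to 2.52 at 18. The smallest margin with 80% power at one-sided 2.5% and equal hazards is exp(2.8016 × 2/√d): 6.47 at 9 events, 3.75 at 18 and 2.78 at 30.

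**6. Events a margin-based PFS test would need.** Margins here are illustrative. Events = 4(z_alpha + z_power)² / (ln margin)², 80% power, equal hazards.

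| Margin (HR) | One-sided 2.5% | One-sided 5% |
|---|---|---|
| 1.3 | 457 | 360 |
| 1.5 | 191 | 151 |
| 2.0 | 66 | 52 |

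For example, 4 × 7.849 / (ln 1.5)² = 31.40 / 0.1644 = 191.0.

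**The case against.** The strongest reply is that this is a pilot. Section 1 says so, Section 2.2 asks Aim 1b only to measure, and Section 11 openly sets 171 per group beside 15. That lowers the practical risk. It does not remove the defect, because Section 11 still commits to testing the hypothesis. A pilot label can excuse low power in a valid test, but it does not turn a test of equality into a test of non-inferiority.

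Several stronger readings are tempting, and the documents do not support them:

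- A reader might infer that the plan intends to declare non-inferiority whenever the logrank p-value exceeds 0.05. No decision rule is written, so the supportable statement is that such a result could be misread that way.
- A reader might infer that non-significance is the only route to the claim. A significant result favouring chemoradiation would also support it.
- A reader might blame the logrank test as such. A logrank-type test can be run against a shifted null, so the real gap is the missing margin.
- A reader might take "without compromising oncologic outcomes" in Section 2 as a PFS requirement for this trial. It describes the general aim of bladder preservation.
- A reader might infer that no PFS margin was ever set. Section 8.2 mentions a Study Synopsis that is not in the available text. Section 11, where a margin belongs, has none.
- A reader might infer that the pilot must fix the larger trial's PFS margin now. Section 11 plans a new sample-size calculation for Aim 2b and does not confine it to quality of life, so this is a matter of judgement.

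**Conclusion.** The plan is wrong as written on this point. It states a PFS non-inferiority hypothesis and assigns it to tests of equality, with no PFS margin in the available documents. Short of demonstrating superiority, neither the logrank test nor the Fisher fallback can establish the claim.

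Under the assumptions in step 2 of the working, none of which comes from the documents except the 15 per arm and the 36 months, a two-sided 5% logrank test would miss a doubled hazard in about 70-80% of trials and a hazard ratio of 1.5 in about 87-90%. The event count of roughly 9-18 is part of those assumptions and is not a trial figure. The logical defect does not depend on it. On precision, even 30 events would give 80% power only for a margin of about 2.8.

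**What to change.** In Section 11, delete the statement that "non-inferiority will be assessed with a logrank test" and the Aim 1b Fisher fallback. Replace them with wording to this effect:

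> Aim 1b is descriptive. Kaplan-Meier curves will be shown by arm. The PFS hazard ratio (chemoradiation to cystectomy, Cox model) and the difference in 3-year Kaplan-Meier PFS will each be reported with a 95% CI. A non-significant logrank or Fisher test is not evidence of non-inferiority. Non-inferiority may be claimed only if the upper confidence limit of the hazard ratio lies below a margin stated in advance.

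Bring the earlier sentence in Section 11 that announces the Aim 1b test into line with this. The deleted wording also covers bladder-intact survival, so the new text should say that it too is reported descriptively; the figures above concern PFS only.

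Optionally, the Aim 2b sample-size calculation could also show PFS event needs for illustrative margins, as in step 6 of the working.

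The cost is a few sentences and one extra model, with no additional patients. The downside is that the pilot gives up a formal PFS non-inferiority claim, which it could not have supported.

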Given the potential non-inferiority of chemoradiation relative to radical cystectomy, clinical prediction of non-response to chemoradiation in terms of biomarkers would be of interest. However, there is paucity of predictive markers that can identify non-responders of chemoradiation. If predictive markers could be identified, patients might then be selected for the treatment most likely to benefit them, which would have the added advantage of maximizing overall cure rates and minimizing poor outcomes. Characterization of the genomic drivers of bladder cancer has been proposed for evaluating progression. Immunohistochemistry has been utilized with limited accuracy. A number of investigators have queried whether comprehensive genomic profiling of cancer-related genes could potentially assist in the selection of targeted therapies for patients with radiation refractory bladder cancer.³ As part of our pilot study, we propose to perform microarray gene expression profiling using Agilent long oligonucleotide (60 mers) technology to search for molecular alterations differing between responders and non-responders of chemoradiation with radical cystectomy as a reference.

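### Section 11 tests biomarkers for significance, with 50 candidate genes in view, but sets no multiplicity control and no exploratory label; at an assumed 5% per gene, about 2.5 false positives are expected on average if no gene differs

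*Combined protocol and SAP*

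**What the plan says.** Section 11 describes the single-marker analysis in one sentence: "The significance of treatment arm differences with regard to biomarkers (Aim 2a) will be assessed with t-tests or Wilcoxon tests". It gives no number of markers, threshold, sidedness or rule for choosing between the two tests. Pairwise correlations and a logistic model follow, with random forests as a fallback.

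The number of genes comes from Section 9.5: "Goal is to study the landscape of 50 important candidate genes, which are involved in bladder cancer". That analysis covers only some patients: "For the participants who have consented to be part of the optional study". The ceiling is set by Section 3.3: "A total of 30 patients will be randomized to either chemoradiation group (n=15) or radical cystectomy", so at most 15 per arm.

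The marker work is a Specific Aim (2a): "To evaluate genetic markers predicting response to chemoradiation by performing tissue RNA microarrays". The word exploratory does not appear. The nearest wording is the pilot label on the whole trial in Section 2.3 and, in Section 1, the intention to "search for molecular alterations differing between responders and non-responders of chemoradiation".

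**The concern.** Testing many genes one by one at an unadjusted level, and describing the outcome as significance, produces nominal findings even when nothing is there. The plan offers no means of telling these from real ones: no adjustment, no ordering of genes and no validation step. MRE11 is introduced in Section 1.1.2 as a candidate with prior evidence, but Section 11 gives it no separate role.

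What is at stake is how the marker results are read. Section 1 gives the motive: "If predictive markers could be identified, patients might then be selected for the treatment most likely to benefit them". With 30 patients or fewer, false leads could be carried into the larger trial that this pilot is meant to inform. The main treatment comparison is not affected.

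**Working it through.** **Inputs**
- Genes: m = 50 (Section 9.5). That each is tested singly is inferred by joining Sections 9.5 and 11.
- Per-gene level: two-sided 0.05, an assumption. The only stated alpha is 5%, for the Aim 1a sample size.
- Group size: at most 15 per arm (Section 3.3), fewer with optional tissue consent (Section 9.5).
- Correlation between genes: not given, so a range is shown.

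**The plan's own figures.** No size, power or error rate is stated for Aim 2a. The Aim 1a figure shows how the plan uses 5%: (0.25 + 0.24) × (1.960 + 0.842)² / 0.15² = 170.9, which rounds up to the stated 171 per group. With one-sided 5% the result is 135. So 5% is used there as two-sided 5%. That makes the assumption for Aim 2a reasonable but does not state it.

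**Expected false positives if no gene differs.** m × alpha = 50 × 0.05 = 2.5. This mean does not depend on correlation. At 0.01 per gene it would be 0.5; at 0.10 it would be 5.

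The exact Wilcoxon test is discrete and slightly conservative:

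| Patients per group | True size | Expected false positives |
|---|---|---|
| 15 | 0.0453 | 2.27 |
| 10 | 0.0433 | 2.16 |
| 5 | 0.0317 | 1.59 |

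**Chance of at least one.** For independent genes, 1 − 0.95^50 = 0.923. The binomial distribution gives 72.1% for two or more and 48.1% for exactly two or three. Simulated t-tests on equicorrelated normal genes, 15 per group:

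| Correlation | At least one p < 0.05 | Any call, Benjamini-Hochberg 5% |
|---|---|---|
| 0 | 0.923 | 0.052 |
| 0.2 | 0.871 | 0.049 |
| 0.5 | 0.639 | 0.042 |
| 0.8 | 0.299 | 0.022 |

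A repeat with exact Wilcoxon tests at 15 per group (8,000 replicates) gave 0.050, 0.041 and 0.024 for Benjamini-Hochberg at correlation 0, 0.5 and 0.8.

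**Is the no-difference case realistic?** Sections 4.1 and 4.2 put the TURBT before the visit at which patients are randomised. Expression in that tissue cannot be affected by the assigned arm, so a significant arm difference in it is a false positive. This does not extend to specimens taken after treatment starts. Section 9.8 also lists blood, and later blood samples could show real arm effects.

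**Choice of test.** Always taking the smaller of the t and Wilcoxon p-values at 15 per group raises the per-test error from 0.0507 to 0.0605.

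**The case against.** The strongest reply is that this is early, small-scale work. Section 2.3 says: "Our study will be a pilot, prospective, single-center, randomized non-inferiority trial comparing chemoradiation therapy to radical cystectomy", and Section 1 speaks of a search. The remark about selecting patients is conditional background, and nothing in the document lets a nominal p-value from this trial determine anyone's treatment. That stands, and it limits the harm. It does not remove the point, because the pilot label describes the trial, while Section 11 says how the markers will be judged and uses the language of significance.

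It is also fair that neither the 50 separate tests nor the 5% level is written into Section 11. Both are inferences and the figures depend on them, but leaving the threshold unstated is part of the gap.

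Three stronger readings are tempting and are not supported:
- *The trial will almost certainly report false markers.* The chance of at least one ranges from about 92% down to about 30%, depending on a correlation the documents do not give.
- *Two or three false markers will appear.* That is an average. Even with independent genes, exactly two or three occurs about 48% of the time.
- *The open choice of t-test or Wilcoxon seriously inflates error.* It moves 5% to about 6%, a minor matter.

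**Conclusion.** The point holds, at moderate weight. Read naturally, the plan runs 50 unadjusted tests with no exploratory label. If no gene differs and each is tested at two-sided 5%, the average is 2.5 false positives (2.27 with exact Wilcoxon at 15 per group, fewer in smaller groups). The chance of at least one is about 92% for independent genes, 64% at correlation 0.5 and 30% at 0.8, so even the most favourable of these is about six times the nominal 5%. For the arm comparison in TURBT tissue, the assumption of no true difference follows from the design.

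A reader might infer that multiplicity control would make the Aim 2a analysis sound. It would not: the aim asks which markers predict response to chemoradiation, whereas the planned tests compare arms. That is a separate issue to settle alongside this one.

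**What to change.** Replace the single-marker sentence in Section 11 with:

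> For each of the 50 candidate genes, log2 expression will be compared between [named groups] with a Wilcoxon rank-sum test. P-values will be adjusted across all 50 genes, including MRE11, by Benjamini-Hochberg, and a gene will be called associated only if its false discovery rate is at most 5%. Effect estimates with confidence intervals will be given for all genes, and all marker results are exploratory.

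The sponsor must fill in the groups: the treatment arms, as now written, or responders and non-responders within the chemoradiation arm, as Aim 2a implies. With no true differences, the chance of any false call is then about 2-5%.

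MRE11 belongs inside the family. The evidence cited for it in Section 1.1.2 concerns survival after radiotherapy compared with cystectomy, not a difference in expression between arms. A looser rule, with a 10% false discovery rate and MRE11 tested unadjusted at 5%, would give a chance of any false call of about 13%, 9% and 6% at correlation 0, 0.5 and 0.8 (15 per group).

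The cost is SAP wording, one line of code and lost sensitivity. A lone gene must reach 0.05/50 = 0.001. For a t-test at 15 per group, that raises the difference detectable with 80% power from about 1.06 to 1.67 SD. Few genes, possibly none, will be called associated at this sample size, which is why the estimates and intervals should be reported for all 50.
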